4.6. Screening Failure

Screening failures are defined as participants who consent to participate in the clinical study but are not subsequently randomized/enrolled in the study. Minimal information includes but is not limited to demography, screening failure details, eligibility criteria, and any serious adverse events.

5. TREATMENTS

5.1. Investigational Medicinal Products Used in the Study

IMP is defined as the test IMPs, reference IMPs, and matching placebo IMPs to the respective test and reference IMPs.

5.1.1. Test Investigational Medicinal Product

The investigational product is a matrix formulation and is designed as a tablet to be administered with food (eg, a snack) and should not be taken on an empty stomach. The IMP is coated with a white polymer coating to aid in swallowing. TEV-50717 tablets have been manufactured according to current Good Manufacturing Practice regulations. TEV-50717 tablets will be supplied as 6-, 9-, 12-, 15-, and 18-mg tablets and will be packaged in blister packs and labeled according to applicable regulatory guidelines. Each blister pack (40-count tablets per dose strength per blister pack) will contain a sufficient supply of drug until the next specified visit/telephone contact, plus overage to account for potential delays in study visits.

Additional details may be found in the IB for TEV-50717.

5.1.1.1. Starting Dose and Dose Levels

Two active-dose levels were selected for this study. The target population, children 6 to 16 years of age, inclusive, will vary considerably in body weight. There will also be varying impairment of the drug metabolizing enzyme CYP2D6, whether from use of certain concomitant medications that inhibit the enzyme or genetic predisposition to poor metabolism of CYP2D6 substrates.

5.1.1.2. Dose Modification and Dose Stratification

As this is a fixed dose study, patients will undergo dose escalation (ie, forced titration) to their target dose over the first 4 weeks of treatment (see Section 3.4 and Table 1). If a patient experiences depression, suicidal ideation or behavior, anxiety, akathisia, parkinsonism, or somnolence, or any other adverse event that interferes with daily activity, or any adverse event that is related to IMP, a single dose reduction is permitted. The investigator must discuss any further dose adjustments (eg, holding the dose or doses) with the medical monitor.

In case of such an adverse event, the investigator will determine if a dose reduction or suspension is necessary. If a determination is made that a dose reduction or suspension is required, the medical monitor must be contacted. All available information, including the patient and caregiver/adult reports of adverse events, the clinical assessment of safety by the investigator, and information from rating scales should be incorporated in the decision. This reduced dose will become the patient's dose for the remainder of the study.

5.1.2. Placebo Investigational Medicinal Product

Placebo tablets match TEV-50717 tablets. The packaging will be the same as described for TEV-50717 above.

Table 3: Investigational Medicinal Products Used in the Study

IMP name	Test IMP	Placebo IMP	Reference IMP (None)
Trade name and INN, if applicable, or company-assigned number	TEV-50717 (previously SD-809), deutetrabenazine	Not applicable	Not applicable
Formulation	film-coated tablet	film-coated tablet	Not applicable
Unit dose strength(s) / Dosage level(s)	TEV-50717 tablets are available in the following dose strengths: 6, 9, 12, 15, and 18 mg, all of which are identical in size, shape, and color (white). IMP will be supplied in 40-count tablets per dose strength per blister pack	Not applicable	Not applicable
Route of administration	oral	oral	Not applicable
Dosing instructions	The total daily dose, as provided in Table 1 , is divided into a twice-daily administration. Two tablets will be taken twice daily starting at day 1 per Table 1 . Daily doses will be administered twice daily, approximately 8 to 10 hours apart during the day. Depending on the dose and arm assigned, TEV-50717 tablets and/or placebo tablets will be taken to maintain the blind. A minimum of 6 hours should elapse between doses. If a patient misses a dose, and it is within 6 hours of their next dose, the missed dose should be skipped. Tablets should be swallowed whole and taken with food (eg, a snack) and should not be taken on an empty stomach.	The total daily dose, as provided in Table 1 , is divided into a twice-daily administration. Two tablets will be taken twice daily starting at day 1 per Table 1 . Daily doses will be administered twice daily, approximately 8 to 10 hours apart during the day. Depending on the dose and arm assigned, TEV-50717 tablets and/or placebo tablets will be taken to maintain the blind. A minimum of 6 hours should elapse between doses. If a patient misses a dose, and it is within 6 hours of their next dose, the missed dose should be skipped. Tablets should be swallowed whole and taken with food (eg, a snack) and should not be taken on an empty stomach.	Not applicable
Packaging	IMP will be provided in blister packs	Placebo IMP will be provided in blister packs	Not applicable
Manufacturer			Not applicable

IMP=Investigational Medicinal Product

5.2. Preparation, Handling, Labeling, Storage, and Accountability for IMPs

5.2.1. Storage and Security

The investigator or designee must confirm appropriate temperature conditions have been maintained for all IMPs received and any discrepancies are reported and resolved before use of the IMPs.

The IMP (TEV-50717 and the placebo) should be stored protected from light, at a controlled room temperature, 20°C to 25°C (68°F to 77°F); however, storage between 15°C and 20°C (59°F and 68°F) is acceptable if there is no alternative. The IMP should be stored in a dry, securely locked, substantially constructed cabinet or enclosure with access limited to authorized staff.

Diversion is considered to have occurred when the legal supply chain of prescription analgesic medicinal products is broken, and medicinal products are transferred from a licit to an illicit channel of distribution or use.

5.2.2. Labeling

Supplies of IMPs will be labeled according to the current International Council for Harmonisation (ICH) guidelines on Good Clinical Practice (GCP) and Good Manufacturing Practice and will include any locally required statements. If necessary, labels will be translated into the local language.

5.2.3. Accountability

Each IMP shipment will include a packing slip listing the contents of the shipment, return instructions, and any applicable forms.

The investigator is responsible for ensuring that deliveries of IMPs and other study materials from the sponsor are correctly received, recorded, handled, and stored safely and properly in accordance with the local regulations, and used in accordance with this protocol.

Only patients enrolled in the study may receive IMPs, and only authorized staff at the investigational center may supply or administer IMPs. All IMPs must be stored in a secure, environmentally controlled, and monitored (manual or automated) area in accordance with the labeled storage conditions or appropriate instructions with access limited to the investigator and authorized staff at the investigational center.

The investigator (or designee) will instruct the patient to store the IMP according to the instructions on the label, if applicable; or will give instructions in an appropriate form.

The investigator, institution, or the head of the medical institution (where applicable) is responsible for IMP accountability, reconciliation, and record maintenance (ie, receipt, reconciliation, and final disposition records).

A record of IMP accountability (ie, IMP and other study materials received, used, retained, returned, or destroyed) must be prepared and signed by the principal investigator or designee, with an account given for any discrepancies. Empty, partially used, and unused blister packs IMP will be disposed of, as agreed with the sponsor/development partner.

5.3. Justification for Investigational Medicinal Products

5.3.1. Justification for Dose of Test Investigational Medicinal Product

As body weight and CYP2D6 impairment are known predictors for exposure to the active circulating metabolites of TEV-50717, the “high” and “low” doses will represent a target exposure (area under the plasma concentration-time curve [AUC], maximum observed concentration (C_{max}) rather than a fixed milligram amount of drug. The high dose targets a mean (CV%) AUC of approximately 1500 ng•hr/mL (60%) and a mean (CV%) C_{max} of approximately 100 ng/mL (39%). These targets were chosen as they represent exposure in another population (HD patients) receiving up to 48 mg/day that was associated with robust efficacy and favorable tolerability. The low dose group targets a mean (CV%) AUC of approximately 1000 ng•hr/mL (60%) and a C_{max} of approximately 80 ng/mL (39%). Based on Phase 3 studies in both HD and TD patients, exposures associated with an AUC of approximately 1000 ng•hr/mL are still anticipated to be efficacious.

5.3.2. Justification for Use of Placebo Investigational Medicinal Product

A standard placebo-controlled, double-blind study design (TEV-50717 [low dose and high dose] vs placebo in a 1:1:1 ratio) was chosen to determine whether IMP treatment results in a statistically significant effect on the tics of patients with TS. As TS is not a progressive neurological disorder, and available treatments are for symptomatic control, the use of placebo is justified in a short-term study where safety is carefully monitored. Moreover, a placebo control is ideal for characterizing the efficacy and safety of an experimental agent in a new study population.

5.4. Treatment after the End of the Study

Patients who complete the study may be eligible to begin participation in an open-label safety extension study of TEV-50717 (Study TV50717-CNS-30047). Patients not participating in the open-label safety extension study for TEV-50717 will have a follow-up telephone contact for safety evaluation 1 week after the end of the treatment period (2 weeks after their last dose of IMP).

5.5. Restrictions

Medications prohibited before and/or during the study are described in Section 5.6.

While patients receiving strong CYP2D6 inhibitors such as paroxetine, fluoxetine, and bupropion at baseline may be enrolled into this study, the removal of strong CYP2D6 inhibitors during treatment is discouraged as this would have an effect on exposure to active circulating drug. If the removal of a strong CYP2D6 inhibitor is required from a clinical perspective, the medical monitor should be contacted so an appropriate change in IMP can be made. The addition of a strong CYP inhibitor is prohibited. The use of quinidine and terbinafine are prohibited (see Appendix H, [Table 11](#)).

Restrictions in regard to sexual activity and required laboratory values are provided in the inclusion and exclusion criteria.

As with other VMAT2 inhibitors (tetrabenazine, reserpine), patients should be advised that the concomitant use of alcohol or other sedating drugs with TEV-50717 may have additive effects and cause or worsen somnolence. Given the age of the study population, the use of alcohol during this study is prohibited.

Patients should be advised not to drive a car or operate dangerous machinery until they understand how TEV-50717 affects them.

Use of illicit drugs is prohibited from the time of signing of the informed consent/assent form and throughout study participation.

Patients may not donate blood from the time of informed consent/assent, while taking the IMP, and for 14 days after the last dose.

5.6. Prior and Concomitant Medication or Therapy

Any prior or concomitant medication a patient has had within 3 months before IMP administration and up to the end of study, including follow-up, will be recorded on the CRF. Generic or trade name, indication, dose, and start and end dates of the administered medication will be recorded. The sponsor will encode all medication according to the World Health Organization (WHO) drug dictionary (WHO Drug).

At each clinic visit after the screening visit, the investigator will ask patients whether they have taken any medications (other than IMP), including over-the-counter medications, vitamins, or herbal or nutritional supplements, since the previous visit. Parents/patients will be instructed during the course of the study to notify the investigator if any new medication is prescribed, including over-the-counter medications. Any prescribed medication should be reviewed with the investigator. Indication, dosage, and start and end dates should be entered on the CRF.

The medical monitor must be contacted if a patient is receiving (or has to begin or stop receiving during the study) a medication that is associated with QTc prolongation or that is a known strong CYP inhibitor. Allowed strong CYP inhibitors at baseline are shown in [Appendix H, Table 8](#). Addition of a strong CYP inhibitor is prohibited.

Prohibited antipsychotic drugs are listed in [Appendix H, Table 9](#). Prohibited medications that are associated with QTc prolongation are listed in [Appendix H, Table 10](#).

Concomitant medication and treatment will be monitored throughout the study.

5.7. Procedures for Monitoring Patient Compliance

The investigator will be responsible for monitoring patient compliance until completion of the IMP administration according to the protocol or discontinuation from IMP. A check of compliance with IMP intake will be performed during each visit after the IMP has been dispensed; and IMP accountability records will be completed.

If the investigator or the sponsor determines that the patient is not in compliance with the study protocol, the investigator and the sponsor should determine whether the patient should be withdrawn from the study. The IEC/IRB should be notified as required by national and local regulations.

Exposure to IMP will be assessed as required.

5.8. Temporary Discontinuation of Investigational Medicinal Product

Dose Reduction

If a patient experiences a “clinically significant” adverse event that is attributed to IMP, the investigator will determine if a dose reduction or suspension is necessary. Dose adjustments should be made based on all available information, including the patient and caregiver/adult reports of adverse events and tic reduction, the clinical assessment of safety and efficacy by the investigator, and information from rating scales. In the case of an adverse event, the investigator is permitted to perform a single dose reduction of 6 mg. **The investigator must discuss any further dose adjustments (eg, holding the dose or doses) with the medical monitor.**

If the determination that a patient requires a dose reduction or suspension is made during a telephone contact, an unscheduled clinic visit should be conducted as soon as practicable thereafter.

Dose Suspension

Suspension of study medication for up to 1 week, if warranted for patient safety, is allowed. If the patient restarts study medication within 7 days of suspension, the full dose of TEV-50717 may be resumed without titration. **Suspensions of study medication for adverse events must be reviewed with the medical monitor before therapy is restarted.** If a subject’s serum potassium or magnesium were tested and found to be below the lower limit of normal and clinically significantly, the laboratory test should be repeated at least once. If the abnormality in the repeated laboratory test is consistent with the prior laboratory test, the IMP must be suspended. The Medical Monitor must be contacted to determine the appropriate investigation and treatment. TEV-50717 may only be restarted once serum potassium or magnesium have normalized.

The reason for a dose reduction or suspension must be clearly documented.

If a dose reduction or suspension occurs before a scheduled clinic visit, the clinic visit will be postponed so that efficacy evaluations can be performed at least 5 days after the change.

The patients who restart IMP treatment will follow the visit schedule as outlined in [Table 2](#). Patients who withdraw from the study will proceed as described in [Section 4.3](#).

5.9. Randomization and Blinding

This is a Phase 3, randomized, double-blind, placebo-controlled, 8-week-treatment study in which patients with tics associated with TS will be invited to participate. Patients will be randomized to either TEV-50717 (low-dose, high-dose) or matching placebo in a 1:1:1 ratio using an Interactive Response Technology (IRT) based on their baseline weight and CYP impairment status. The patients will be stratified into 2 age groups (6 to 11 years and 12 to 16 years). Patients and investigators will remain blinded to treatment assignment during the study.

Patients will be centrally randomly assigned to the treatment groups by means of a computer-generated randomization list after confirmation of all eligibility criteria. The creation of the randomization list will be under the responsibility and oversight of Syneos Health.

In addition, the sponsor's clinical personnel and all vendors (with exception of the IRT vendor and the bioanalytical sample analysis vendor) involved in the study will be blinded to the IMP identity until the database is locked for analysis and the treatment assignment revealed. After unblinding of this study, the study site may remain blinded to patient treatment assignments until completion of the safety extension Study TV50717-CNS-30047.

The randomization list and treatment will be assigned to the relevant treatment groups through a qualified service provider (ie, via IRT). The generation of the medication list and management of the IRT system will be done by a qualified service provider under the oversight of Nuvelution TS Pharma, INC (referred to hereafter as Nuvelution TS Pharma).

The staff member at the investigational center who will dispense the IMP will not know the treatment given to each patient.

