
A secondary objective is to evaluate the safety and tolerability of TEV-50717.
	
The safety endpoints are as follows:
 
 • incidence of adverse events • observed values and changes from baseline in vital signs • observed values and change from baseline in the Children’s Depression Inventory Second Edition (CDI-2; Parent and Self-report Profiles) • observed values in the children’s Columbia Suicide Severity Rating Scale (C-SSRS) • observed values and changes from baseline in electrocardiogram (ECG) parameters and shifts from baseline for clinically significant abnormal findings • observed values and changes from screening in clinical laboratory parameters (hematology, chemistry, and urinalysis) 
In addition to routine monitoring of adverse events, clinical laboratory

Objectives	Endpoints
	parameters, 12-lead ECGs and safety scales, an independent Data Monitoring Committee will monitor safety during the conduct of the study.

Pharmacokinetic Endpoint:

The pharmacokinetics of the alpha-dihydrotrabenazine (α -HTBZ) and beta-dihydrotrabenazine (β -HTBZ) metabolites of TEV-50717 will be explored based on sparse sampling (2 samples) at week 8.

General Study Design: This is a Phase 3, randomized, double-blind, placebo-controlled, 8-week treatment study in which patients with tics associated with TS will be invited to participate. Patients will be randomized to low-dose TEV-50717, high-dose TEV-50717, or placebo (1:1:1). The target dose for each patient receiving TEV-50717 will be based on the group to which they are randomized, body weight at baseline, and cytochrome P450 2D6 (CYP2D6) impairment status. Patients will be classified as CYP2D6 impaired if they are receiving a strong CYP2D6 inhibitor or are a CYP2D6 poor metabolizer based on blinded assessment of CYP2D6 genotype at baseline. CYP2D6 status will be used by Interactive Response Technology (IRT) for randomization into the study.

Prescreening period (up to 3 months before baseline): For patients who require discontinuation of certain prohibited concomitant medications 3 months before baseline (depot neuroleptics, botulinum toxin, or trabenazine), informed consent/assent, depending on the child's age, as appropriate, should be obtained prior to discontinuing the prohibited medication.

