3.4. Drug Administration

IMP will be administered as follows:

- IMP should be swallowed whole and taken with food (eg, a snack) and should not be taken on an empty stomach.
- Dosing will be based on body weight and CYP2D6 impairment status at the baseline visit, as shown in Table 1.
- The total daily dose, as provided in Table 1, is divided into a twice-daily administration. Two tablets will be taken twice daily starting at day 1 per Table 1. Daily doses will be administered twice daily, approximately 8 to 10 hours apart during the day. Depending on the dose and arm assigned, TEV-50717 tablets and/or placebo tablets will be taken to maintain the blind. A minimum of 6 hours should elapse between doses. If a patient misses a dose, and it is within 6 hours of their next dose, the missed dose should be skipped.
- After week 1, dose escalations may not occur more frequently than once every 5 days.
- The dose of IMP will be escalated weekly during the escalation period, according to Table 1.
- In the case of an adverse event, the investigator is permitted to perform a single dose reduction of 6 mg. **The investigator must discuss any further dose adjustments (eg, holding the dose or doses) with the medical monitor.**
- During the titration period, the dose of the IMP will be adjusted weekly according to Table 1. Investigators will be blinded to CYP status, with a dose cap for poor metabolizers prespecified by the IRT.

IMP will be packaged in blister packs and provided for patients to take at home (see Section 5.1).

Table 1: Daily Dose of IMP by Baseline Body Weight Category, CYP2D6 Impairment, and Study Week

Dose group Baseline weight (kg)	Daily dose (mg) at the start of visit/week ^a			
	Week 1 (Days 1-7)	Week 2 (Days 8-14)	Week 3 (Days 15-21)	Week 4 main dose (Days 22-28) to Week 8 main dose (Days 50-56)
Low dose				
≥40	12	24	30	36
≥40, CYP impaired	6	12	18	18
30 to <40	6	12	18	24
30 to <40, CYP impaired	6	12	12	12
20 to <30	6	12	18	18
20 to <30, CYP impaired	6	6	6	6
High dose				
≥40	12	24	36	48
≥40, CYP impaired	6	15	24	30
30 to <40	12	24	30	36
30 to <40, CYP impaired	6	12	18	18
20 to <30	12	18	24	30
20 to <30, CYP impaired	6	12	12	12

^a Administration of a given dose will take place throughout the days indicated. The new dose starts the morning after the telephone contact or the morning after the clinic visit.

CYP impaired=patients who are receiving a strong CYP2D6 inhibitor or who are a CYP2D6 poor metabolizer.

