5.10. Maintenance of Randomization and Blinding

Patients will be randomly assigned to receive treatment with TEV-50717 (low dose, high dose) or matching placebo in a 1:1:1 ratio using an IRT based on their baseline weight and CYP impairment status. The patients will be stratified into 2 age groups (6- to 11-years and 12- to 16-years). The sponsor will monitor enrollment in age strata to ensure there is adequate representation in each stratum. Patients and investigators will remain blinded to treatment assignment during the study. In addition, the sponsor's clinical personnel and all vendors (with the exception of the IRT vendor and the bioanalytical sample analysis vendor) involved in the study will be blinded to the IMP identity until the database has been locked for analysis and the treatment assignments are revealed. However, if a prioritized sample analysis is needed, bioanalytical personnel may be unblinded.

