## 8.2. Primary Efficacy Endpoint and Analysis

### 8.2.1. Primary Efficacy Analysis

The primary analysis will be a mixed-model, repeated-measures with the change in the TTS as the dependent variable. The model will include fixed effects for treatment group, week (3 levels: weeks 2, 4, and 8), and the treatment group by week interaction. The baseline TTS, region, and age group at baseline (2 levels: 6-11 year, 12-16 years) will be included as covariates. The unstructured covariance matrix for repeated observations within patients will be used. In case that the model does not converge, the Maximum-Likelihood estimation method will be used instead of the default Restricted Maximum-Likelihood. If the model still does not converge, then a simpler covariance structure with fewer parameters will be used, according to the following order: Heterogeneous Autoregressive (1), Heterogeneous Compound Symmetry, Autoregressive (1), and Compound Symmetry. The Kenward-Roger approximation will be used to estimate denominator degrees of freedom.

The least squares means of the change in TTS from baseline at week 8 will be compared (primary: TEV-50717 high-dose arm vs. the placebo arm; secondary: TEV-50717 low-dose arm vs. the placebo arm) using 2-sided tests at the alpha=0.05 level of significance. The SAS code for this test is as follows:

The least square (LS) mean and standard error for the treatment groups, and the LS mean difference, 95% confidence interval (CI), and p-value for each comparison (TEV-50717 high-dose vs. placebo at week 8; TEV-50717 low-dose vs. placebo at week 8) will be presented.

Cohen's d effect size will also be computed for each comparison (Kelley, 2007). Cohen's d is calculated as:

$$d = (\mu_t - \mu_p) / (\text{pooled SD}),$$

where  $\mu_t$  represents the least-square (LS) mean of the specified TEV-50717 group (High- or Low-dose),  $\mu_p$  is the LS mean of the placebo group, and the pooled SD is based on the adjusted LS means and adjusted standard errors from the mixed-effect model for MMRM, specifically:

$$\text{Pooled SD} = \frac{\text{Standard Error (SE)}}{\sqrt{\frac{1}{nt} + \frac{1}{np}}}$$

and nt=number of patients in specified TEV-50717 group and np=number of patients in placebo group.

The utility of Cohen's d is to help judge the clinical importance of a measured treatment difference.

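### Randomization is described as using baseline weight and CYP2D6 status, but the primary model contains neither: settle their role, then add them to the model or correct the text

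*Protocol*

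**What the plan says.** **Randomization.** Protocol 5.9 says patients are allocated 1:1:1 by the IRT "based on their baseline weight and CYP impairment status". It then adds: "The patients will be stratified into 2 age groups (6 to 11 years and 12 to 16 years". The synopsis, Protocol 5.10 and SAP 3.7 use essentially the same pair of statements. The synopsis also states: "CYP2D6 status will be used by Interactive Response Technology (IRT) for randomization into the study". Protocol 3.1 and SAP 3.4 say much the same about CYP2D6 status.

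**Other uses of the two factors.** Protocol 3.4 says: "Dosing will be based on body weight and CYP2D6 impairment status at the baseline visit". Table 1 of both documents sets the daily dose by three weight bands crossed with CYP2D6 impairment. Protocol 5.3.1 gives the reason: "body weight and CYP2D6 impairment are known predictors for exposure to the active circulating metabolites".

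**Primary model.** SAP 8.2.1 fits an MMRM with treatment, week and their interaction, and says: "The baseline TTS, region, and age group at baseline (2 levels: 6-11 year, 12-16 years) will be included as covariates". Protocol 9.5.5.1 lists the same covariates. The MMRMs for TS-CGI and the C&A-GTS-QOL ADL subscale (SAP 8.3.1) follow this model with their own baseline value. In the readable efficacy text, CYP2D6 status appears only as a subgroup for summarizing the tic score (SAP 8.2.3). SAP 12 does not comment on the difference between the randomization text and the model.

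**The concern.** An analysis should normally reflect the factors on which the randomization was balanced. When balance is forced on a prognostic factor, the treatment estimate varies less from trial to trial. A model that omits the factor leaves its variance in the residual, so the reported standard error does not show that gain. The estimate stays unbiased, but the confidence interval is wider than it need be, the test rejects too rarely under the null, and some power is lost.

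Of the three factors named in the randomization text, only age group is in the model. If weight and CYP2D6 status were balanced by design, the model is incomplete. If they were not, the randomization text misdescribes the design. A reader of the two documents cannot tell which randomization was run, and a confirmatory plan should say.

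**Working it through.** **1. Reproduce the plan's sample size.** Inputs from Protocol 9.1: difference 6.5, SD 9.5, two-sided alpha 0.05, power at least 90%, about 50 per arm.

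n = 2 × (9.5/6.5)² × (1.960 + 1.282)² = 44.9, so 45 evaluable per arm. The plan gives no dropout rate. With an assumed 10%, 45/0.90 = 50, which matches the plan.

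SAP 8.2.2 reports 8% overall early termination. That leaves 50 × 0.92 = 46 per arm, for which the two-sample t-test power is 90.1%.

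**2. Inputs for the omitted factors.** Let r be the share of residual variance in week-8 change that weight and CYP2D6 status explain together. The documents give no value. I assume 2%, 5% and 10%.

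**3. Formulas if both factors are balanced by design.**

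- SE reported without the factors: 9.5 × √(2/46) = 1.981
- True SE: 1.981 × √(1 − r)
- Overstatement ratio: 1/√(1 − r)
- True type I error: 2 × [1 − Φ(1.96/√(1 − r))]
- Power: noncentral t with 90 df and noncentrality 6.5/true SE. The critical value is 1.987 with the factors in the model and 1.987/√(1 − r) without them. The loss of 3 df is ignored.

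**4. Results.**

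| r | True SE | SE overstated by | Type I error | Power without the factors | Power with them | Gain (points) |
|---|---|---|---|---|---|---|
| 2% | 1.961 | 1.0% | 4.8% | 90.3% | 90.6% | 0.3 |
| 5% | 1.931 | 2.6% | 4.4% | 90.6% | 91.5% | 0.8 |
| 10% | 1.879 | 5.4% | 3.9% | 91.2% | 92.8% | 1.6 |

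Gains are taken before rounding.

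**5. Simulation check.** There were 6,000 trials per scenario, with 150 patients in three arms, permuted blocks of 3, and an ANCOVA at one visit standing in for the MMRM. The age and weight mix and a 12% CYP2D6-impaired share were assumed.

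- Strata of age, weight and CYP2D6: at r = 5%, the age-only model had type I error 4.3% and power 93.4%, against 94.2% with the factors added. At r = 10% the figures were 4.1%, and 93.6% against 94.9%. At r = 0 the two models did not differ (92.1% power each).
- Age the only stratum: the age-only model's mean SE was 1.90 at every r and agreed with the empirical SE within simulation error. Type I error was 4.6% to 4.8%.

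Power is higher here than in step 4 because all 50 patients per arm are analysed.

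**The case against.** The strongest reply is that age is the only stated stratum and it is already in the model. Both documents apply the word stratified only to the age groups, and monitoring refers to age alone: "The sponsor will monitor enrollment in age strata to ensure there is adequate representation in each stratum". Weight and CYP2D6 status have a separate documented job, which is setting the dose, so the IRT needs them whether or not they enter the allocation list. This stands as a genuine alternative reading. It does not settle the matter, because the synopsis, Protocol 3.1 and SAP 3.4 say specifically that CYP2D6 status is used for randomization.

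A second reply is that neither document shows either factor to predict change in TTS. Protocol 5.3.1 calls them predictors of exposure, and the dosing scheme is designed to offset that. Weight also overlaps with age group. This stands too: r could be close to zero, and then nothing is lost.

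Third, the sensitivity analyses in SAP 8.2.2 and the primary model code are redacted or not shown. The two factors may be examined there, which cannot be checked.

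Three stronger readings are tempting but unsupported:

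- A reader might infer that the standard error is definitely wrong. It is not if age is the only stratum.
- A reader might infer that age is the only adjustment. The model also has baseline TTS and region.
- A reader might set the adjusted powers in step 4 against the 90.1% baseline and claim gains of 0.5, 1.4 and 2.7 points. That mixes two designs. If the factors are strata, the unadjusted test also gains from the balance.

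**Conclusion.** The mismatch between the randomization text and the model is real, and its statistical consequence is conditional and small. The consequence requires that allocation was balanced on weight and CYP2D6 status, and that these predict change in TTS beyond the covariates already in the model. Under both conditions, with an assumed 2% to 10% of residual variance explained, the standard error is overstated by 1.0% to 5.4%, type I error is about 4.8% to 3.9% instead of 5%, and 0.3 to 1.6 points of power are given up at 46 per arm. The error is in the conservative direction: there is no bias and no inflated false-positive risk, and the planned 50 per arm stands. If the first condition fails, the primary analysis is valid as written and the defect lies in the description of the randomization. Some change is needed on either reading.

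**What to change.** Before unblinding, confirm against the IRT specification whether weight category and CYP2D6 status entered the allocation, and record the answer.

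- If they did, add weight category (20 to <30, 30 to <40, ≥40 kg) and CYP2D6 impairment (yes/no) as fixed effects in SAP 8.2.1 and in the TS-CGI and ADL models that refer to it, and note the change in SAP 12. The low-dose TTS comparison comes from the same primary model, so it is covered. The cost is 3 degrees of freedom (2 for weight, 1 for CYP2D6). Both variables are already collected, and the sample size does not change.
- If the IRT used them only to select the dose kit, leave the model alone and correct the synopsis, Protocol 3.1, 5.9 and 5.10, and SAP 3.4 and 3.7. They should say that randomization is stratified by age group only and that weight and CYP2D6 status determine the dose within the assigned arm. The cost is a wording change.
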